The Effectiveness of the Video Conferencing Telerehabilitation Method, Delivered in One on One and Group Sessions, in Urinary Incontinence Cases.

Study Protocol and Statistical Analysis Plan (SAP) (Pages 1 – 21)

November 15,2021

**The Effectiveness of the Video Conferencing
Telerehabilitation Method, Delivered in One on One and Group Sessions, in Urinary
Incontinence Cases.**

Study Protocol (Pages 2-6)

November 15,2021

Study Protocol

Study titled “The Effectiveness of the Video Conferencing Telerehabilitation Method, Delivered in One on One and Group Sessions, in Urinary Incontinence Cases.” was approved by Marmara University Faculty of Medicine Ethical Committee at the meeting on 30.11.2020 with approval number: 1195 (Annex-1).

The legal representatives of the patients who participated in the study will be informed about the aim, duration and the programs to be applied throughout the study. Volunteer Information Form will be signed and approved in accordance with the standards deemed appropriate by the Ethical Committee of Marmara University Faculty of Medicine. The study will be conducted in accordance with the Declaration of Helsinki.

Hypothesis of the Study

H0: With one on one video conference method, exercise training is no superiority of exercise training with group video conferencing method in urinary incontinence.

H1: Exercise training with one on one video conference method is more effective in increasing muscle strength in patients with urinary incontinence.

H2: One on one videoconferencing and exercise training are more effective in reducing the degree of incontinence in patients with urinary incontinence.

H3: Exercise training with one on one videoconferencing method is more effective in increasing the quality of life in patients with urinary incontinence.

H4: Exercise training with one on one videoconferencing method is more effective in increasing patient satisfaction in patients with urinary incontinence.

H5: Exercise training with one on one video conference method is more effective in increasing sexual function in patients with urinary incontinence.

H6: Exercise training with one on one videoconferencing method is more effective in increasing exercise adherence in patients with urinary incontinence.

Randomization of the Study Groups

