Individuals with Urinary İncontinence applying to Göztepe [name]. Süleyman Yalçın Şehir Hastanesi will be invited to participate in the study. Individuals who volunteered to participate and whom met the criteria for participation will be randomized with simple random sampling method and will be

divided into two groups. In both groups participants will receive same exercise program and physiotherapist will follow up the exercise program every week by video conference method. While only the physiotherapist and the patient will take part in the one-on-one group, there will be a physiotherapist and 8 patients in the group sessions.

Inclusion Criteria

18-65 aged

BMI 18-30 kg/m²

Being diagnosed with stress incontinence or mixed incontinence (dominantly SUI)

Mild or moderate incontinence (mild SUI; urinary incontinence with coughing, sneezing, laughing, or any strenuous activity. Moderate; urinary incontinence with carrying, pushing, lifting, walking, and any light physical activity)

Exclusion Criteria

Pregnancy

Ongoing vulvovaginitis or urinary tract infection or malignancy

Pelvic floor muscle strength is between 0-1 according to the Modified Oxford Scale,

Previous surgery for SUI

Problems with vision or inability to understand given commands

Conservative therapy in the last 6 months

Allergic reaction to the gel used with the perinometer/probe

Evaluations

Evaluation parameters will be applied at the baseline, at the end of 4-weeks treatment program, at the end of 8 weeks treatment program. Outcome measures and applied evaluations are shown in Table 1.

Table 1. Outcome measures and evaluation methods

Primary Outcome Measures	Evaluation Methods
Muscle Strength	-PERFECT Scheme -Surface Electromyography

Secondary Outcome Measures	Evaluation Methods
Symptom Evaluation	-1 hour pad test -The International Consultation on Incontinence Questionnaire-Short Form - Urogenital Distress Inventory- 6 (UDI-6) - Incontinence Impact Questionnaire-7 (IIQ-7) - Overactive Bladder -Validated 8- Question Awareness Tool (OAB-V8)
Patient Satisfaction	Visual Analog Scale (VAS)
Exercise Adherence	VAS Broome Pelvic Floor Muscle Exercise Self- Efficacy Scale
Sexual Function	Female Sexual Function Scale (FSFI)

Treatment Program

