The exercises which given the both groups compose same exercise protocols for 8 week. The exercise protocol includes pelvic floor muscle training, diaphragmatic breathing exercise and core exercise will be given the all participants. The participants in the study will be followed up with video conferencing method by weekly.

Group I (one on one video conferencing group): In this group, exercise follow-up and transition to the next exercise phase will be realized with one-on-one video conference interviews.

Group II (group sessions video conferencing group): In this group, exercise follow-up and transition to the next exercise stage will be realized with group video conference sessions consisting of 8 participants.

The Effectiveness of the Video Conferencing Telerehabilitation Method, Delivered in One on One and Group Sessions, in Urinary Incontinence Cases.

Statistical Analysis Plan (SAP) (Pages 7 –8)

November 15,2021

Statistical Analysis Plan (SAP)

In the analysis of the data to be obtained in the study, the significance will be evaluated at the $p < 0.05$ level with the SPSS 22.0 statistical program at the 90% confidence interval. In the evaluation of variables; If the number of cases is sufficient, its conformity to the normal distribution will be questioned with the Kolmogorov Smirnov test and normal distribution graphs. In the examination of the variables, appropriate statistical tests will be applied depending on the provision of parametric or non-parametric test conditions. Normally distributed variables will be expressed as mean and standard deviation, and non-normally distributed variables will be expressed as numbers and percentages. If the groups fit the normal distribution, the evaluation results at the beginning, 4th week and 8th week will be compared with ANOVA, if the normal distribution is not met, comparisons will be made with Kruskal Wallis and appropriate post-hoc tests. In the correlation analysis, the appropriate Spearman or Pearson correlation analysis methods will be preferred. Chi-square test will be used in the evaluation of binary data.

The Effectiveness of the Video Conferencing Telerehabilitation Method, Delivered in One on One and Group Sessions, in Urinary Incontinence Cases.

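### The hypotheses compare one-on-one with group delivery, but for continuous and ordinal outcomes the SAP states no arm contrast and no deciding visit

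*Combined protocol and SAP*

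**What the plan says.** The question is between arms. Hypothesis of the Study opens with "H0: With one on one video conference method, exercise training is no superiority of exercise training with group video conferencing method in urinary incontinence". The first alternative, on the primary outcome domain, is "H1: Exercise training with one on one video conference method is more effective in increasing muscle strength in patients with urinary incontinence", and H2 to H6 follow the same pattern. Under Randomization of the Study Groups, participants are randomised to two arms, and "In both groups participants will receive same exercise program". Evaluations schedules baseline, week 4 and week 8. Neither Table 1 nor any hypothesis attaches a visit to an outcome.

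The Statistical Analysis Plan is a single paragraph. Its clauses on comparing outcomes are:

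- a general clause: "appropriate statistical tests will be applied depending on the provision of parametric or non-parametric test conditions";
- for normal data: "If the groups fit the normal distribution, the evaluation results at the beginning, 4th week and 8th week will be compared with ANOVA";
- otherwise: "comparisons will be made with Kruskal Wallis and appropriate post-hoc tests";
- for binary data: "Chi-square test will be used in the evaluation of binary data".

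The paragraph also mentions correlation analysis, which is not a comparison of arms.

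**The concern.** A trial that randomises two arms to learn which is better needs a stated estimate or test of the difference between them, at a stated time. For continuous and ordinal outcomes the SAP gives neither. What it lists for comparison is three time points.

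Three things are at stake.

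- Both arms do the same exercises, so both are expected to improve. A significant change over visits says nothing about which mode of delivery is better.
- Kruskal-Wallis assumes independent groups. Applied across visits, it would treat three measurements on one participant as three different people.
- The sentence can be read in several ways that give different tests, and the choice among them could be made after the data are seen.

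A separate misfit affects H4 and part of H6. The satisfaction items (Annex 7) and the adherence VAS (Annex 8) ask about treatment already received. They have no meaningful baseline, so a comparison from baseline to week 8 does not suit them.

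**Working it through.** The plan gives no figure to reproduce: no sample size, gain, SD or visit correlation. **Assumed throughout:** 16, 24 or 32 per arm; SD 1; equal correlation ρ of 0.5 or 0.7 between visits; independent participants; two-sided 5% tests. Half of the week-8 gain is reached by week 4.

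**1. Across visits, arms pooled.** Compare equal arms (gains 0.5 and 0.5 SD) with different arms (0.75 and 0.25 SD). The pooled mean gain is (0.5 + 0.5)/2 = 0.5 in the first case and (0.75 + 0.25)/2 = 0.5 in the second, so the pooled visit means are identical. Simulated share of trials with p<0.05:

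| Test | Arms equal | Arms differ by 0.5 SD |
|---|---|---|
| Kruskal-Wallis across visits | 24–73% | 22–71% |
| Repeated-measures ANOVA across visits | 69–100% | 68–100% |
| ANCOVA between arms, week 8 | 5% | 34–79% |
| Group-by-visit ANOVA, interaction | 5% | 22–63% |

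Only the last two rows respond to an arm difference.

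**2. Across visits, within each arm.** Take equal gains of 0.5 SD, so visit means are 0, 0.25 and 0.5 and their squared deviations sum to 0.0625 + 0 + 0.0625 = 0.125. The noncentrality of the repeated-measures F test is λ = n × 0.125/(1 − ρ), with 2 and 2(n − 1) degrees of freedom. This gives the chance p that one arm is significant. The chance that exactly one of two equal arms is significant is 2p(1 − p).

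| n per arm | ρ | λ | p | 2p(1 − p) |
|---|---|---|---|---|
| 16 | 0.5 | 4.00 | 0.380 | 47% |
| 16 | 0.7 | 6.67 | 0.586 | 49% |
| 24 | 0.5 | 6.00 | 0.555 | 49% |
| 24 | 0.7 | 10.00 | 0.788 | 33% |
| 32 | 0.5 | 8.00 | 0.695 | 42% |
| 32 | 0.7 | 13.33 | 0.901 | 18% |

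Simulations of this set-up gave similar ranges, with lower ends of 16–18% and upper ends of 46–49%.

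**3. Kruskal-Wallis across visits within one arm.** With no change over time, the simulated rejection rate is 0.03–0.5% instead of 5%, so the test is conservative. Its power against Friedman is 6–29% v 31–77% for a gain of 0.5 SD, and 67–99% v 85–100% for 1.0 SD. The loss shrinks as the gain grows.

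**4. Arms compared at each visit.** Two independent 5% tests would give 1 − 0.95² = 9.75%. Weeks 4 and 8 are correlated, and the simulated rate of two-sided p<0.05 at either visit under the null is 8.1–9.5%. About half of that, 4–5%, favours one-on-one. One visit named in advance gives 5%, of which half favours one-on-one.

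**5. Group-by-visit ANOVA.** This answers the question for normal outcomes (last row of the first table). Kruskal-Wallis is a one-factor test with no interaction, so the fallback does not match it. The fallback may well be needed for the primary outcome. The exclusion criterion "Pelvic floor muscle strength is between 0-1 according to the Modified Oxford Scale" grades strength on an ordinal scale, so an ordinal Power score in the PERFECT scheme is plausible, though this is an assumption.

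**6. Sessions of eight.** Adding an assumed Group II session effect at week 8 with variance 0.05 or 0.10 SD² moves the size of the week-8 ANCOVA from 5% to about 7–9% or 10–13%.

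**The case against.** The strongest reply is that the sentence begins with a condition on the groups, a word the protocol uses for the arms, and that Kruskal-Wallis is itself an independent-groups test. An arm comparison at each visit may therefore be intended. With two arms Kruskal-Wallis is equivalent to the Mann-Whitney test, so this would be workable. A group-by-visit ANOVA is also possible, since the type of ANOVA is not given. Its fallback could be Kruskal-Wallis on change scores.

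These readings are possible but not stated. The arms appear only in the normality condition, while the things compared are results at three times. Post-hoc tests fit three visits; two arms need none. Even if the arms are meant, no visit is named as deciding, and no change score is specified. The general clause names no test, contrast or visit, and the chi-square clause does not reach muscle strength as measured.

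Four stronger inferences are tempting, and the documents do not support them.

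- That the sponsor will not compare the arms. The text is silent on this; it does not exclude it.
- That a test across visits never responds to an arm difference. This is so only with the arms pooled. Within-arm tests do respond, but setting their p-values side by side is not a valid arm comparison.
- That 8–9.5% is the rate of false superiority claims. The hypotheses are directional and the SAP does not state sidedness; the rate in favour of one-on-one is about 4–5%.
- That the reading will be chosen after the data are seen. It could be; nothing says when.

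**Conclusion.** The point stands and should be settled before any outcome is analysed. As written, the SAP does not fix how its primary hypothesis will be tested, and its most natural reading tests something else. That conclusion rests on the wording alone.

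The sizes are illustrative and depend on assumed inputs. A within-arm reading makes exactly one of two equal arms significant in roughly one trial in six to one in two. A per-visit reading without a named visit raises two-sided false significance from 5% to about 8–9.5%. Kruskal-Wallis across positively correlated visits is conservative and loses power, most when gains are modest.

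It would also go too far to call any between-arm test valid as it stands. Group II is treated in sessions of eight, so the arm tests keep their nominal size only if session effects are negligible, which the documents do not establish. The pages between the SAP and Annex 2 were not available for this check.

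**What to change.** Replace the ANOVA/Kruskal-Wallis sentence with wording such as:

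> For each outcome with a baseline value, the arms will be compared at one named visit (for example week 8) with a baseline-adjusted model: ANCOVA, or a mixed model with arm, visit, arm × visit and baseline. The arm difference at that visit, with its confidence interval, is the deciding contrast; the other post-baseline visit is supportive. For ordinal or clearly non-normal outcomes, the arms will be compared at the same visit with a rank-based or ordinal between-arm test, preferably baseline-adjusted. The satisfaction and adherence VAS will be compared directly between arms at that visit. Within-arm change over visits is descriptive; if tested, repeated-measures ANOVA or Friedman will be used, not Kruskal-Wallis.

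The essential part is one arm contrast at one visit per outcome. Week 8 and ANCOVA are suggestions; a prespecified group-by-visit ANOVA would also serve for normal outcomes. Unless session effects can be taken as negligible, the contrast should account for session in Group II.

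The cost is SAP wording, because all three assessments are already scheduled. Accounting for session also needs each Group II participant's session to be recorded. The downside is that the sponsor commits in advance to one visit and one contrast per outcome.

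### Comparing the three visits by ANOVA or Kruskal-Wallis ignores pairing, and outcome-related dropout would distort change over time and, if unequal between arms, the arm comparison

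*Combined protocol and SAP*

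**What the plan says.** The Evaluations section has the same patients measured three times: "Evaluation parameters will be applied at the baseline, at the end of 4-weeks treatment program, at the end of 8 weeks treatment program". Under Randomization of the Study Groups they are "divided into two groups", one followed individually and the other in sessions of eight.

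The SAP's only rule for the repeated results, which first supposes normality, starts "the evaluation results at the beginning, 4th week and 8th week will be compared with ANOVA, if the normal distribution is not met, comparisons will"; for that second case it names Kruskal-Wallis with post-hoc tests. The software is SPSS 22.0. The SAP section does not give the type of ANOVA, an arm-by-visit term, an analysis population, a rule for missed visits or an expected dropout rate.

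The hypotheses concern the arms. H1, for example, reads: "Exercise training with one on one video conference method is more effective in increasing muscle strength in patients with urinary incontinence".

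**The concern.** With two arms, visit is the only factor with three levels in the SAP sentence, and post-hoc tests have a purpose only with three or more groups. The natural reading is therefore that the three visits are compared with each other. Kruskal-Wallis is a test for independent samples, and so is ANOVA if run one-way. Neither uses the fact that the same patients recur. Once anyone withdraws, the baseline sample holds everyone and the week-8 sample only those who stayed.

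If ANOVA means the repeated-measures GLM procedure in SPSS, pairing is respected, but a patient who misses one visit is removed with all her observed data.

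On either reading the result depends on who left. If leaving is related to outcome, the change in muscle strength and in every repeated symptom score is distorted. If it also differs between the two formats, the distortion enters the comparison that the trial exists to make.

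**Working it through.** **Inputs.** From the documents: two arms, three visits, the two named tests, SPSS 22.0. No sample size, dropout rate or visit correlation is given in the text available, so there is no figure to reproduce. Everything below is an assumption, with no true change in anyone, a standardised outcome (SD 1) and higher meaning better.

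**1. Visits as independent samples: shift in the week-8 mean.** If the lowest fraction d of a standard normal variable is removed, the mean of the rest is φ(z_d)/(1−d):

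- d = 5%: 0.109
- d = 10%: 0.195
- d = 20%: 0.350
- d = 25%: 0.424

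Let c be the correlation between the tendency to leave and baseline strength, and r the correlation between baseline and week 8. The spurious week-8 shift against the full baseline sample is r × c × φ(z_d)/(1−d).

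| Dropout | c | r = 0.5 | r = 0.7 |
|---|---|---|---|
| 10% | 1 | 0.10 | 0.14 |
| 20% | 1 | 0.18 (0.350 × 0.5 = 0.175) | 0.25 (0.350 × 0.7 = 0.245) |
| 10% | 0.5 | 0.05 | 0.07 |
| 20% | 0.5 | 0.09 | 0.12 |

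**2. Unequal dropout between arms.** With 5% versus 25% dropout and c = 0.5: 0.5 × (0.424 − 0.109) = 0.158. Multiplied by r this is 0.158 × 0.5 = 0.08 SD to 0.158 × 0.7 = 0.11 SD, against the arm that keeps more patients.

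**3. Simulation with a different dropout rule.** Sixty patients, r = 0.5 or 0.7, leaving after week 4 according to a noisy version of the week-4 result.

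- *Worst patients leave:* the available-data gain was 0.08 to 0.12 SD at 10% dropout, 0.16 to 0.22 at 20% and 0.22 to 0.31 at 30%.
- *Best patients leave:* about the same size with the opposite sign.
- *Random dropout:* about zero.
- *Two arms of 30, r = 0.6:* equal selective dropout (20%/20%) gave no bias (0.001 SD). Unequal dropout (5%/25% or 10%/30%) gave 0.16 SD. This exceeds step 2 because selection here is much stronger: the dropout score correlates 1/√1.25 = 0.894 with week 4, and 0.894 × 0.6 × (0.424 − 0.109) = 0.17.

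**4. Significance.** Because pairing is ignored, Kruskal-Wallis is very conservative: it rejected in 0 to 0.7% of runs with no dropout or random dropout. With the worst leaving it rejected in about 3% of runs at 20% dropout and 9 to 16% at 30%. The distortion therefore shows mainly in the means. The same conservatism costs sensitivity to real change even with no dropout.

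**5. Repeated-measures GLM.** If each later visit is missed independently with probability m, the share deleted is 1 − (1 − m)²: 19% at m = 10% and 27.8% at m = 15%. For pure withdrawal, a patient who leaves before week 4 also misses week 8, so the loss is only the week-8 dropout fraction. In the simulation with the worst 20% at week 4 leaving, the completer test rejected a true null in 14 to 19% of runs, although the completers' baseline-to-week-8 change averaged about zero; among completers it is the week-4 mean that is raised.

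**6. Are completers' paired changes a safe substitute?** No. At 20% dropout with equal correlations:

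- If the lowest at baseline leave, the paired change is −0.350 × (1 − r), or −0.18 SD at r = 0.5 and about −0.10 SD at r = 0.7.
- If those who improved least by week 4 leave, it is 0.350 × √((1 − r)/2), or +0.18 SD at r = 0.5 and +0.14 SD at r = 0.7.

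**7. After the change.** A likelihood analysis of all observed visits stayed within about 0.01 SD of the true zero in every scenario of step 3, where dropout depended on observed values plus random noise.

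**The case against.** The SAP sentence conditions on the groups being normally distributed and never says what is compared with what. It could mean arm against arm at each visit, which is what H1 to H6 need. False improvement over time would then drop out, leaving only bias from selective dropout that is unequal between arms. This reading is possible, although Kruskal-Wallis with post-hoc tests is an odd choice for two groups. It also leaves the missed-visit rule and the analysis population unstated.

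Several stronger statements are tempting, and the documents do not support them.

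- *That these tests can never cope with withdrawals, or that withdrawal always looks like improvement.* Random dropout gives no bias, the sign reverses if patients doing well leave, and ANOVA after imputation would be possible, though none is planned.
- *That the shift is 0.35 SD at 20% dropout, or 0.16 SD between arms at 5% versus 25% with c = 0.5.* Those figures require week-8 scores to correlate perfectly with baseline.
- *That withdrawals of 10% or 15% would delete 19% or 28% of patients.* That holds for independent missed visits only.

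The normal-tail formula is also approximate for the PERFECT power grade. That scale is short and ordinal, and the exclusion criteria already remove Oxford grades 0 to 1. Finally, the pages between the SAP section and Annex 2 were not available. The SAP section reads as complete, but a rule there cannot be excluded.

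These points limit the size and direction of the problem. They do not make an independent-samples test suitable for paired visits.

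**Conclusion.** The point stands in conditional form and merits a change to the SAP. Read naturally, the plan applies an independent-samples test to repeated measurements, or a procedure that discards incomplete patients, and it names no between-arm contrast for the hypotheses. Loss of pairing applies whatever the dropout. Bias over time needs dropout related to outcome. Bias between arms needs that dropout to be unequal as well, which is plausible because the formats differ but is not documented.

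The actual size is unknown. Under the baseline-dropout assumptions of steps 1 and 2, it is about 0.18 to 0.25 SD for the week-8 shift and 0.08 to 0.11 SD between arms. Weaker selection gives less. Selection that follows the week-4 result closely can give more between arms, about 0.16 SD.

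**What to change.** Replace the ANOVA/Kruskal-Wallis sentence with the following, before outcome data are examined by arm.

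- **Main model.** One linear mixed model (SPSS MIXED) per repeatedly measured outcome, with baseline, week-4 and week-8 values all as outcomes. Fixed effects are visit and arm-by-visit, with baseline means constrained equal across arms (that is, arm terms at weeks 4 and 8 only), and visits correlated within patient.
- **Population.** Every randomised participant with any observed value, in the assigned arm. Putting baseline among the outcomes, not using it as a covariate, keeps those who leave before week 4 in the model.
- **Test.** The week-8 arm difference for each hypothesis. Within-arm change comes from the same model, not from completers' paired values.
- **Ordinal or clearly skewed scores.** A rank-based or ordinal version of the model.
- **Satisfaction and adherence VAS.** Compare the arms directly. The items in Annexes 7 and 8 ask about treatment already received, so they have no meaningful baseline.
- **Sensitivity analysis.** One that allows dropout to depend on unobserved values, for example missing week-8 values set to the patient's baseline. This is a single fixed assumption and should be reported as such.

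The cost is SAP wording and a little more analysis work; no extra data are collected. The downside is that the main model assumes dropout is explained by observed values. Clustering within the eight-patient sessions is a separate matter that this change does not settle.

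### The SAP specifies no baseline adjustment for outcomes measured before treatment, which costs precision and leaves conditional bias when the arms differ by chance at baseline

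*Combined protocol and SAP*

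**What the plan says.** The Evaluations section sets three assessment times: "Evaluation parameters will be applied at the baseline, at the end of 4-weeks treatment program, at the end of 8 weeks treatment program". Table 1 makes muscle strength, by PERFECT scheme and surface EMG, the primary outcome. The secondary outcomes are the pad test, symptom questionnaires, satisfaction, adherence, self-efficacy and sexual function.

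The SAP has one rule for comparing these results. Under normality, "the evaluation results at the beginning, 4th week and 8th week will be compared with ANOVA"; otherwise, "if the normal distribution is not met, comparisons will be made with Kruskal Wallis and appropriate post-hoc tests". A more general sentence says that "appropriate statistical tests will be applied depending on the provision of parametric or non-parametric test conditions". Correlation analysis and a chi-square test are the only other analyses listed. No covariate, change score, mixed model or arm-by-visit term is named.

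Under Randomization of the Study Groups, participants "will be randomized with simple random sampling method". No stratification factor is given. H1 to H6 claim that one-on-one sessions do better, so the comparison of interest is between arms.

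**The concern.** Under simple allocation the arms can differ by chance in starting strength or leakage. Eligibility excludes only the lowest Modified Oxford grades and admits stress or mixed, mild or moderate incontinence, so starting values can vary. The stated analysis does nothing specified about such a difference.

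A participant's own baseline also usually predicts her later value. If it does so here, leaving it out of the model makes the arm difference less precise than the collected data allow. At stake is power that would cost no extra patient, and protection against a result that partly reflects where the arms started. Fixing the model beforehand also prevents a later choice between adjusted and unadjusted results.

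**Working it through.** **Inputs.** From the documents: two arms; assessments at baseline, week 4 and week 8; significance level 0.05. The documents give no sample size, SD, effect size, allocation ratio, sidedness or baseline-to-follow-up correlation ρ, so there is no planned figure to reproduce. Assumed: 24 per arm, 1:1, two-sided test, SD 1 at every visit, the same ρ between any two visits, and a true difference of 0.6 SD at week 8. Where week 4 enters the power calculation, its difference is 0.3 SD.

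**Step 1: precision of the week-8 arm difference.** Variance relative to week 8 alone:
- follow-up only: 1
- change from baseline: 2(1−ρ)
- baseline as covariate: 1−ρ²

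At ρ = 0.4, 0.6 and 0.8, change gives 1.20, 0.80 and 0.40; adjustment gives 0.84, 0.64 and 0.36. Adjustment is below follow-up only for any ρ above 0. It is below change for any ρ below 1, because 2(1−ρ)/(1−ρ²) = 2/(1+ρ), which exceeds 1.

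**Step 2: power.** For a one-degree-of-freedom contrast with relative variance v, the noncentrality is 0.6/√(2v/24). For the arm effect averaged over three visits, the mean difference is (0+0.3+0.6)/3 = 0.3 and v = (1+2ρ)/3. For the arm-by-visit F test (2 and 92 df), λ = 12 × 0.18/(1−ρ) = 3.6, 5.4 and 10.8, where 0.18 is the sum of squared deviations of 0, 0.3 and 0.6 from their mean.

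| Analysis | ρ = 0.4 | ρ = 0.6 | ρ = 0.8 |
|---|---|---|---|
| Week 8, unadjusted (noncentrality 2.08) | 53% | 53% | 53% |
| Change to week 8 (1.90, 2.32, 3.29) | 46% | 62% | 90% |
| Week 8, baseline-adjusted (2.27, 2.60, 3.46) | 60% | 72% | 92% |
| Arm effect averaged over three visits (1.34, 1.21, 1.12) | 26% | 22% | 19% |
| Arm-by-visit interaction | 37% | 52% | 83% |

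At ρ = 0.3 adjustment gives 57% (noncentrality 0.6/√(2 × 0.91/24) = 2.18) against 53% unadjusted.

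**Step 3: how often imbalance arises.** The chance of a baseline difference above 0.3 SD is 2·P(Z > 0.3/√(2/n)). It is 40%, 30% and 23% for n = 16, 24 and 32 per arm (Z = 0.85, 1.04 and 1.20).

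**Step 4: what an imbalance does.** For a baseline difference b, the estimate shifts by ρb (follow-up only), (ρ−1)b (change), (1+2ρ)b/3 (three-visit average) and 0 (adjusted). With ρ = 0.6 and b = 0.3 SD:
- follow-up only: 0.6 × 0.3 = +0.18 SD
- change: −0.4 × 0.3 = −0.12 SD
- three-visit average: 2.2 × 0.3/3 = +0.22 SD
- adjusted: 0

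**Step 5: type I error.** In a simulation with 24 per arm, ρ = 0.6, no true effect and 6,000 runs, overall rejection was 4.8% to 5.2% for every method. Among runs with an absolute baseline difference of at least 0.3 SD (31% of runs), it was 11.5% for follow-up only, 8.5% for change, 8.1% for the interaction, 15.7% for the three-visit average and 4.7% for baseline adjustment.

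**The case against.** The strongest objection is that the SAP sentence is too vague to convict. It may mean separate comparisons at each visit, an arm effect over three visits or an arm-by-visit analysis, and the clause on suitable tests does not rule out adjustment. This stands as far as it goes: a reader might infer that the plan definitely models baseline as a visit level, and the text does not establish that. But the clause ties test choice only to parametric conditions, Kruskal-Wallis takes no covariate, and none of the three readings includes adjustment. If only within-arm change over time is meant, there is no arm comparison at all, which is a separate and larger gap.

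Second, a reader might infer that baseline is misplaced whatever contrast is chosen. That is not so. A longitudinal model that keeps baseline as a response and gives both arms a common baseline mean has essentially the precision of covariate adjustment. Change and interaction contrasts also use each participant's baseline. They over-correct, but at high correlation the residue is small (variance 0.40 against 0.36 at ρ = 0.8). An interaction test can even match a week-8 adjusted test when the full effect is already present at week 4, because it also uses the week-4 data: simulated power at ρ = 0.8 was 92.1% against 91.4%. The advantage of adjustment holds for the same contrast on the same data.

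Third, the documents do not establish the size of the gain. No source is given for ρ, and the eligibility limits on strength and severity may narrow the baseline range and lower it. This stands.

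**Conclusion.** The omission is clear from the text: no baseline adjustment is specified for outcomes that are measured before treatment. On every between-arm reading of the ANOVA, the same contrast would be estimated more precisely with adjustment, and some bias remains once the arms differ by chance at baseline.

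The size rests on assumptions. With 24 per arm and 0.6 SD at week 8, adjustment adds about 7, 19 and 39 percentage points of power over unadjusted follow-up at ρ = 0.4, 0.6 and 0.8, and about 14, 10 and 3 points over change from baseline (from unrounded powers). At ρ = 0.3 the gain over unadjusted is about 4 points. The low powers for the three-visit average apply only if that is the ANOVA meant.

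A reader might infer an invalid test. The calculations do not support that: over all randomisations each method holds about 5%. This is a free improvement in efficiency and in protection against chance imbalance, not a failure of validity.

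**What to change.** Keep the provision for non-normal data and add a paragraph to the SAP that does the following:

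- For each outcome with a valid pre-treatment value (muscle strength, pad test, symptom questionnaires, self-efficacy, FSFI), take the week-8 arm difference and its confidence interval from a model of the week-4 and week-8 values. Include arm, visit, arm-by-visit, baseline value and baseline-by-visit, and allow for within-participant correlation, for example with an unstructured covariance. A model that keeps baseline as a response with a common baseline mean across arms is an acceptable equivalent.
- For ordinal or clearly non-normal outcomes, such as PERFECT power, use a baseline-adjusted rank-based or ordinal equivalent.
- For satisfaction (Annex 7) and the adherence VAS (Annex 8), keep an unadjusted between-arm comparison. Their items ask about treatment already received, so they have no valid baseline.
- Add incontinence type and severity as covariates only if the screening classification is captured as data. A reader might assume that it is, because both are eligibility criteria, but the Patient Evaluation Form (Annex 2) has no field for either.

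The cost is one SAP paragraph, with no new visit, patient or outcome measurement. Using type and severity would need two fields on the form. Allowing for clustering within the eight-patient sessions is a separate point that the same model would have to accommodate.
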